### **5.5.3 Vital Signs Data**

Vital signs include body temperature, respiration rate, pulse, systolic blood pressure, and diastolic blood pressure in supine and standing position. In addition, body weight and waist circumference are measured. The potential clinically relevant vital sign abnormalities will be listed by subject. Criteria for the potentially clinically relevant vital sign abnormalities are provided in [Appendix 2](#). Incidences of clinical relevant vital signs abnormalities based on the observation from the scheduled and unscheduled post-baseline visits will be tabulated for the safety sample. In addition to waist circumference and weight, vitals sign parameters at each visit, and change from baseline at the post-baseline visits will be summarized for the safety sample. Body weight changes will be evaluated for the safety sample by calculating mean change from baseline and by tabulating the incidence of  $\geq 7\%$  weight gain or loss by visit.

If vital sign assessments are repeated for the same visit, the last repeat values are used for production of summary tables. This is accomplished by sorting patient data by visit date and visit time (if applicable) within the same visit identification.

### **5.5.4 Electrocardiograms (ECG) Data**

All ECG analyses are made using observed data. Baseline is defined as average of ECG measurements at baseline visit as specified in [Section 5.1.2](#). Last visit is defined as defined as average of ECG measurements at last visit as specified in [Section 5.1.2](#). Missing ECG data are not imputed. For the calculation of QT correction by heart rate, QTc is missing only if all 3 consecutive beats are unreadable. As long as there is at least 1 beat available in the lead, the data are included in the analysis. For each ECG, QT and RR intervals from three consecutive complexes (representing three consecutive heart beats) are measured manually. The QT correction is performed on beat-to-beat basis. The mean of ratios (beat-to-beat) is calculated by  $(QTc1 + QTc2 + QTc3)/3$  using each

QT-RR pair: (QT1, RR1), (QT2, RR2) and (QT3, RR3). The corrected QT intervals for QTcB, QTcF, and QTcN are defined as follows:

- QTcB is the length of the QT interval corrected for heart rate by Bazett's formula:  $QTcB = QT / (RR)^{1/2}$ .
- QTcF is the length of the QT interval corrected for heart rate by Fredericia's formula:  $QTcF = QT / (RR)^{1/3}$ .
- QTcN is the length of the QT interval corrected for heart rate by the FDA Neuropharm Division formula:  $QTcN = QT/(RR)^{0.37}$ .

Potentially clinically relevant ECG abnormalities will be listed by subject. Criteria for potentially clinically relevant ECG abnormalities are provided in [Appendix 3](#). The incidences of abnormal ECGs of potentially clinical relevance based on the observation at the scheduled and the unscheduled post-baseline visits will be tabulated for the safety sample. Descriptive statistics of change from baseline in heart rate and ECG intervals of PR, QRS, RR, QT, QTcB, QTcF, and QTcN will be presented for each scheduled visit and last visit for the safety sample, respectively.

In summarizing the incidence of abnormalities, a subject must have had an evaluation that meets abnormality criteria by the end of trial. Incidence rate will be calculated as the number of subjects having at least one abnormality within the trial divided by the number of subjects who are both exposed to trial medication and have an on-treatment evaluation. In addition, incidences of categorical change in ECG - QTc will be provided for change from baseline >30 millisecond, change from baseline >60 millisecond, new onset >450 millisecond, new onset >480 millisecond and new onset >500 millisecond for the safety sample. Change from baseline in ECG parameters will be calculated at scheduled visit and last visit for the safety sample.

If ECG assessments are repeated for the same visit, the last repeat values are used for production of mean change from baseline. This is accomplished by sorting subject data by visit date and visit time (if applicable) within the same visit identification.

### **5.5.5 Physical Examination**

Physical examination findings will be listed by subject.

### **5.5.6 Other Safety Data Analysis**

#### **5.5.6.1 Special Interested Adverse Events**

Incidence of treatment emergent adverse events of special interest, including EPS-related AEs, weight-related AEs, glucose-related AEs, lipid-related AEs, white blood cell abnormalities, orthostasis, prolactin-related AEs, QT-interval AEs, suicidality-related

AEs, and injection-site-related AEs, will be tabulated for safety sample. In addition, proportion of subjects received anticholinergic medication for treatment-emergent EPS-related events will be assessed for safety sample.

### **5.5.6.2 Extrapyramidal Symptoms Rating Scales**

Extrapyramidal symptoms rating scales included the SAS, AIMS, and the BARS. The SAS total score (range 10 to 50) is the sum of the rating scores for 10 items from the SAS panel in the CRF. The AIMS movement rating score (range 0 to 28) is the sum of the rating scores for facial and oral movements (items 1 to 4), extremity movements (items 5 and 6), and trunk movements (item 7). A missing value of any item for the SAS or the AIMS movement scale could result in a missing SAS total score or AIMS movement rating score. The BARS global score (range 0 to 5) is derived from the global clinical assessment of akathisia from the BARS panel in the CRF. Mean changes from baseline on the SAS total score, AIMS movement score, and the BARS global score will be summarized by visit in descriptive statistics.

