1.3 Known and Potential Risks and Benefits

As of 01 Jun 2014, all voluntary reports of adverse events (AEs) in patients taking aripiprazole received since market introduction that were considered by the sponsor as medically relevant have been listed in the USPI and EU SmPC ([Appendix 13](#)). The USPI and EU SmPC also contain the currently available phase 2/3/4 clinical safety information ([Appendix 13](#)). Across the short-term, double-blind, placebo-controlled studies conducted in schizophrenic subjects, the AE profile of oral aripiprazole was generally comparable to that of placebo. There was little difference in the incidence of discontinuation due to AEs between aripiprazole-treated (7%) and placebo-treated (9%) subjects. Akathisia was the only commonly observed AE that occurred in $\geq 5\%$ of aripiprazole-treated subjects and at an incidence more than twice that of placebo (8% vs. 4%, respectively). Aripiprazole was well-tolerated in the long-term studies. Changes in body weight, fasting glucose, lipid profile, and serum prolactin levels were similar between aripiprazole- and placebo-treated subjects. No clinically relevant changes in QTc were observed in either group.¹⁶ In the pooled analysis of the two 52-week studies comparing aripiprazole with haloperidol, the incidence of EPS-related AEs was significantly higher for haloperidol (58%) compared with aripiprazole (27%). In the one 52-week study in which prolactin levels were measured, significantly fewer aripiprazole-treated subjects (3.4%) experienced prolactin elevations above the upper limit of normal compared with the haloperidol group (61%).¹⁸

The comparative safety profile of oral aripiprazole relative to placebo in subjects with acute bipolar mania raised no new safety concerns and was similar to that observed in

Protocol 31-10-270

subjects with schizophrenia. Additionally, aripiprazole exhibited a more favorable safety profile than haloperidol in the 26-week active-controlled study in acute bipolar mania. The safety profile was consistent with that observed in haloperidol-controlled schizophrenia studies, as evidenced by a lower incidence of AE discontinuation; EPS-related AEs, and prolactin elevation.²²

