11.	Subjects with a history of neuroleptic malignant syndrome or clinically significant tardive dyskinesia at screening.

Protocol 31-10-270

Table 3.4.3-1 Exclusion Criteria	
Prohibited Therapies and/or Medications	
12.	Subjects likely to require prohibited concomitant therapy during the trial (see Table 4.1-1).
13.	Subjects who may require cytochrome P450 (CYP) 2D6 or CYP3A4 inhibitors or CYP3A4 inducers during the trial (see Table 4.1-1 and Section 4.2.1).
14.	Any subject who requires or may need any other antipsychotic medications during the course of the study.
Other Exclusion Criteria	
15.	Prisoners or subjects who are compulsorily detained (involuntarily incarcerated) for any reason must not be enrolled into this trial.
16.	Electroconvulsive therapy within 180 days prior to entry.
17.	Aripiprazole IM Depot (including generic formulation) is commercially available in the subject's country.

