7.4 Secondary Outcome Measures

Mean change from baseline of vital signs parameters, laboratory tests, and ECG parameters will be provided by visit. Incidence of clinically significant abnormalities in vital signs parameters, laboratory tests, and ECG parameters will be tabulated.

Percentage of subjects showing significant weight gain or loss from enrollment to endpoint (significant weight change is defined as a $\geq 7\%$ increase or decrease in weight) will be provided. Injection site reactions will be summarized by visit using the mean of VAS subject-reported rating scores and investigator's rating of local pain, swelling, redness and induration at the injection site. Data collected on the C-SSRS will be summarized by visit also.

Mean and mean change from baseline in the efficacy endpoint CGI-S score will be summarized by visit. Descriptive statistics of EPS will be provided by calculating mean change from baseline in AIMS, SAS, and BARS. Results will be summarized by visit.

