4. GLOBAL CLINICAL ASSESSMENT OF AKATHISIA

- 0 = Absent - No evidence of awareness of restlessness. Observation of characteristic movement of akathisia in the absence of a subjective report of inner restlessness or compulsive desire to move the legs should be classified as pseudoakathisia
- 1 = Questionable - Non specific inner tension and fidgety movements
- 2 = Mild akathisia - Awareness of restlessness in the legs and/or inner restlessness worse when required to stand still. Fidgety movement present, but characteristic restless movements of akathisia not necessarily observed. Condition causes little or no distress.
- 3 = Moderate akathisia - Awareness of restlessness as described for mild akathisia above, combined with characteristic restless movements; finds the condition distressing
- 4 = Marked akathisia - Subjective experience of restlessness includes a compulsive desire to walk or pace. However, the patient is able to remain seated for at least five minutes. Constant restlessness which is associated with intense distress and insomnia
- 5 = Severe akathisia - The patient reports a strong compulsion to pace up and down most of the time. Unable to sit or lie down for more than a few minutes. Constant restlessness which is associated with intense distress and insomnia.

Adapted from Barnes TR. Br J Psychiatry. 1989;154:672-6.

Protocol 31-10-270

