## **5 Statistical Method**

### **5.1 Data/Data Sets Specifications**

#### **5.1.1 Data Sets Analyzed**

The following analysis samples are defined for this trial:

- Enrolled Sample: All subjects who sign the informed consents form for the trial and enter the trial.
- Safety Sample: All subjects who receive at least one dose of open-label aripiprazole IM depot.
- Efficacy Sample: All subjects who enter and have at least one post-baseline efficacy evaluation.

Due to the open-label single-arm nature of the trial, all endpoints will be summarized using descriptive statistics. Continuing variables will be tabulated for frequency, mean, median, standard deviation (SD), maximum and minimum. Categorical variables will be tabulated for frequency and percentage. No formal statistical analyses are planned due to the open-label nature of this trial. Subjects who enrolled in this trial rolled over directly from Trial 248. Subjects who enrolled in Trial 248 either rolled over from Trial 31-07-246 or Trial 31-07-247, or directly entered Trial 31-08-248 as *de novo* subjects (i.e., subjects never enrolled in Trial 31-07-246 or 31-07-247). The data will be summarized by enrollment source into Trial 248 as well for all subjects.

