## Appendix 4 Table of Contents for Tables and Listings

### Clinical Summary Tables

CT-1.1	SUBJECT DISPOSITION
CT-1.2	SUBJECT DISPOSITION BY REGION, COUNTRY AND CENTER
CT-1.3	SUBJECT DURATION BY MONTH
CT-1.4	ENROLLMENT BY COUNTRY
CT-1.5	ENROLLMENT BY COUNTRY BY AGE GROUP
CT-2	REASONS FOR DISCONTINUATION
CT-3	DEMOGRAPHIC CHARACTERISTICS BY SEX
CT-4.1	CONCOMITANT MEDICATIONS TAKEN PRIOR TO STUDY PERIOD
CT-4.2	CONCOMITANT MEDICATIONS TAKEN DURING STUDY PERIOD
CT-4.3	CONCOMITANT MEDICATIONS TAKEN POST STUDY PERIOD
CT-4.4	CONCOMITANT BENZODIAZEPINES AND ANTICHOLINERGICS USE
CT-5	CGI SEVERITY SCORE - MEAN CHANGE FROM BASELINE BY MONTH - OC
CT-6.1.1	SIMPSON-ANGUS SCALE TOTAL SCORE - MEAN CHANGE FROM BASELINE BY MONTH - OC
CT-6.1.2	BARNES AKATHISIA GLOBAL SCORE - MEAN CHANGE FROM BASELINE BY MONTH - OC
CT-6.1.3	AIMS MOVEMENT RATING SCORE - MEAN CHANGE FROM BASELINE BY MONTH - OC
CT-6.2.1	COLUMBIA-SUICIDE SEVERITY RATING SCALE (C-SSRS) - INCIDENCE OF SUICIDALITY
CT-6.2.2	COLUMBIA-SUICIDE SEVERITY RATING SCALE (C-SSRS) - INCIDENCE OF SUICIDALITY BY TYPE
CT-6.2.3	COLUMBIA-SUICIDE SEVERITY RATING SCALE (C-SSRS) - MEAN CHANGE FROM BASELINE IN SUICIDAL IDEATION INTENSITY TOTAL SCORE
CT-7.1	EXTENT OF EXPOSURE TO STUDY MEDICATION - ARIPIPRAZOLE IM DEPOT
CT-7.2	DESCRIPTIVE STATISTICS FOR STUDY DAYS OF ARIPIPRAZOLE IM DEPOT INJECTIONS
CT-7.3	EXTENT OF EXPOSURE TO STUDY MEDICATION BY INJECTION DOSE - ARIPIPRAZOLE IM DEPOT
CT-8.1	INCIDENCE OF ADVERSE EVENTS (ALL CAUSALITIES)
CT-8.2.1	INCIDENCE OF TREATMENT-EMERGENT ADVERSE EVENTS BY SYSTEM ORGAN CLASS
CT-8.2.2	INCIDENCE OF TREATMENT-EMERGENT ADVERSE EVENTS BY SYSTEM ORGAN CLASS AND MEDDRA PREFERRED TERM
CT-8.2.3	INCIDENCE OF TREATMENT-EMERGENT ADVERSE EVENTS BY SYSTEM ORGAN CLASS, MEDDRA PREFERRED TERM AND SEVERITY
CT-8.2.4.1	INCIDENCE OF TREATMENT-EMERGENT ADVERSE EVENTS GREATER THAN 5% BY SYSTEM ORGAN CLASS AND MEDDRA PREFERRED TERM
CT-8.2.4.2	INCIDENCE OF TREATMENT-EMERGENT ADVERSE EVENTS BY MEDDRA PREFERRED TERM IN DESCENDING ORDER OF INCIDENCE RATE FOR TOTAL
CT-8.2.4.3	INCIDENCE OF NON-SERIOUS TREATMENT-EMERGENT ADVERSE EVENTS OCCURRING IN AT LEAST 5% OF THE SUBJECTS BY SYSTEM ORGAN CLASS AND MEDDRA PREFERRED TERM
CT-8.2.4.4	OCCURRENCE (NUMBER OF EVENTS) OF NON-SERIOUS TREATMENT-EMERGENT ADVERSE EVENTS BY SYSTEM ORGAN CLASS AND MEDDRA PREFERRED TERM
CT-8.2.5	INCIDENCE OF TREATMENT-EMERGENT EPS ADVERSE EVENTS

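### The AIMS, SAS and BARS ratings are summarised only as mean changes, so a rated rise in akathisia or abnormal movement that is not reported as an adverse event is counted in no table

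*SAP*

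**What the plan says.** Protocol 7.4 gives the three scales a single form of summary: "Descriptive statistics of EPS will be provided by calculating mean change from baseline in AIMS, SAS, and BARS". SAP 5.5.6.2 carries this over: "Mean changes from baseline on the SAS total score, AIMS movement score, and the BARS global score will be summarized by visit". The summarised scores are the SAS total (10 to 50), the AIMS movement score from items 1 to 7 (0 to 28) and the BARS global score (0 to 5). SAP Appendix 4 has one table per scale, CT-6.1.1 to CT-6.1.3. The BARS table is titled "BARNES AKATHISIA GLOBAL SCORE - MEAN CHANGE FROM BASELINE BY MONTH - OC". The general convention in SAP 5.1.1 adds the usual statistics: "Continuing variables will be tabulated for frequency, mean, median, standard deviation (SD), maximum and minimum".

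EPS is also followed through adverse events. SAP 5.5.6.1 tabulates "Incidence of treatment emergent adverse events of special interest, including EPS-related AEs", and also the proportion of subjects given anticholinergics for such events. CT-8.2.5 reports EPS adverse events; CT-8.2.2 and CT-8.2.3 report all treatment-emergent events by preferred term and by severity. The individual ratings are listed in PDATA-16.1 to PDATA-16.3.

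The rating forms carry severity anchors. BARS item 4 in Protocol Appendix 9 has "2 = Mild akathisia - Awareness of restlessness in the legs and/or inner restlessness worse when required to stand still". On the AIMS form in Protocol Appendix 7, a score of 2 on items 1 to 9 means mild, and item 8 rates the overall severity of abnormal movements.

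**The concern.** Drug-induced akathisia or dyskinesia would be expected as a clear rise in a few subjects rather than a small shift in everyone. A mean over all rated subjects is a poor display of that pattern, and it never says how many subjects were affected.

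The question matters in this trial. EPS is a named safety endpoint (Protocol 3.5.1), and collecting long-term safety data is the secondary objective. Protocol 1.3 says "Akathisia was the only commonly observed AE" to meet its criterion of at least 5% incidence and more than twice placebo. The visit schedule runs to Month 104, which is 104 × 28 = 2,912 days, or about 8 years, so late abnormal movements could be seen. Exclusion criterion 11 reads "Subjects with a history of neuroleptic malignant syndrome or clinically significant tardive dyskinesia at screening", so clinically significant dyskinesia rated during the study should mostly be new. If the adverse event tables miss some of these subjects, the scale tables as planned will not recover the number.

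**Working it through.** **Figures to reproduce.** The plan states no EPS rate, threshold, power or sample size formula. Only the score ranges can be checked, and they are right: SAS 10 × 1 to 10 × 5 = 10 to 50; AIMS 7 × 0 to 7 × 4 = 0 to 28.

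**Step 1: how the SAP treats comparable data.**

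| Data | Subject-level count or proportion planned? | SAP section |
|---|---|---|
| Laboratory tests | Yes | 5.5.2 |
| Vital signs, weight change of 7% or more | Yes | 5.5.3 |
| QTc categories | Yes | 5.5.4 |
| C-SSRS emergence and worsening | Yes | 5.5.6.3 |
| Investigator's injection-site rating, four levels | Yes, proportion per level | 5.5.6.4 |
| AIMS, SAS, BARS | No, mean change by visit | 5.5.6.2 |

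AIMS items 8 to 10 and BARS items 1 to 3 are collected but enter no planned summary table.

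**Step 2: does the adverse event route pick up every raised rating?** Adverse events are elicited by an open, non-leading question (Protocol 5.2). For two other kinds of finding the protocol states a conversion rule. A laboratory value the investigator judges an abnormal change from baseline counts as an adverse event (Protocol 5.1), and so does a condition newly found at a later physical examination (Protocol 3.6.3.3.1). Protocol 3.6.3.5 and its subsections contain no such rule for AIMS, SAS or BARS. The anticholinergic proportion in SAP 5.5.6.1 is defined on EPS-related events, so it depends on the same reporting.

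**Step 3: dilution in the mean.** Assume a share p of subjects rises by d points and the rest do not change. Then mean change = p × d and SD = d × √(p(1 − p)). Both p and d are assumptions, because the documents give no scale distributions.

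- BARS global, p = 8%: mean 0.08 × 2 = +0.16 (SD 0.54) to 0.08 × 3 = +0.24 (SD 0.81), which is 3.2% to 4.8% of the 0 to 5 range.
- BARS global, p = 3% to 10%, d = 2 to 3: mean +0.06 to +0.30, or 1.2% to 6.0% of the range.
- AIMS movement score, p = 3% to 10%, d = 3 to 6: mean +0.09 to +0.60, or 0.3% to 2.1% of the 0 to 28 range.
- Net zero needs offsetting improvement. With 8% rising by 2 points, 16% would have to fall by 1 point (0.16 × 1 = 0.16), or 8% by 2 points.

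The value p = 8% is borrowed from Protocol 1.3, where it is the akathisia adverse event rate on oral aripiprazole in short-term placebo-controlled studies (4% on placebo). It is not a BARS rate.

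**Step 4: what the other planned statistics show.** If well under half of the subjects change, the median change can stay at 0. The maximum shows one subject, and the SD shows spread. None gives the number affected. By-visit summaries also cannot give a cumulative count, because subjects whose symptoms arise and resolve around different six-monthly visits never appear together in one row.

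**Step 5: what a count would show.** If everyone is below 2 at baseline, any rise of 2 or more points crosses the threshold, so the count returns p directly. At p = 8% that is 40 of 500 or 64 of 800 subjects, with approximate 95% intervals of 5.6% to 10.4% and 6.1% to 9.9%.

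**The case against.** The case against is substantial, and much of it stands.

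A reader might infer that the SAP has no count of subjects who develop akathisia or dyskinesia. The documents do not support that: SAP 5.5.6.1, directly before the section at issue, counts EPS-related events per subject, with CT-8.2.5, CT-8.2.2 and CT-8.2.3 behind it. SAP 5.5.7.1 also reports overall anticholinergic use. A reader might also infer that a minority signal averages out to about zero. Step 3 shows a small positive mean. Exact cancellation would need a sizeable group entering with raised scores and then improving, which fits poorly with most subjects starting near the floor.

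For akathisia the unreported group is probably small, though its size is unknown. BARS subjective items are elicited by direct questioning at visits where adverse events are also recorded. The level-2 anchor includes awareness of restlessness, and the adverse event definition is broad. The 8% itself came from adverse event reporting.

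Finally, the SAP follows the protocol's stated summary faithfully. The study is single-arm and descriptive, the primary measures are adverse events, and the ratings are listed.

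This does not remove the gap. No text ties a raised rating to an adverse event, a listing is not a summary, and medication use says nothing about untreated ratings. The argument is strongest for dyskinesia: item 10 of the AIMS form provides for a subject with no awareness of the movements, and an open question about how the subject has felt can miss exactly that case.

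**Conclusion.** The concern holds in a limited form. The rated EPS data are summarised only as mean change by visit, and no planned table gives the number of subjects who newly reach a rated level of akathisia or abnormal movement. EPS adverse events are counted, so what goes uncounted is the raised rating that is not reported as an adverse event, chiefly dyskinesia. The documents do not allow the size of that group to be estimated.

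The effect of averaging is dilution to a small value, and the figures in step 3 only illustrate it. They rest on assumed shares and rises, and on an 8% that comes from a different route of administration, a shorter duration and a different measure. Severity is low: this is a reporting gap in a descriptive study, not an error or a missing EPS incidence analysis.

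**What to change.** Keep CT-6.1.1 to CT-6.1.3 unchanged. Add to SAP 5.5.6.2 and Appendix 4 the number and percentage of subjects whose worst post-baseline rating, scheduled or unscheduled, meets each of the following:

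- BARS global score of 2 or more, with baseline below 2. This is the form's own anchor for mild akathisia.
- AIMS item 8 of 2 or more, with baseline below 2. This is the form's anchor for mild. The documents define no AIMS case criterion, so the sponsor should confirm it as a reporting threshold.

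Use as denominator the subjects below the threshold at baseline who have at least one post-baseline rating. Accompany each count with a baseline-by-worst shift table. No SAS cut-off is proposed, because the documents give none.

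These are reporting thresholds and change no treatment or withdrawal rule. The cost is SAP wording and two short tables from data already collected. The downside is that the counts may look less favourable than the means.
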